| Provided that lifetime AED history be collected | To aid in interpretation of efficacy and safety findings | 
 • Section 9.5.1.2 • Table 5 |
| Added details of the handling and assay of PK samples | For clarity and completeness | 
 • Section 9.5.1.4 |
| CCI CCI | CCI CCI CCI | 
 • Section 9.5.1.6 • Section 9.7.1.9 |
| Clarified that Follow-up Visit intervals will have a window of ±2 days | To allow sufficient flexibility in scheduling visits | 
 • Table 5 |
| Clarified that the minimum interval of 10 days between visits does not apply to Visit 3 | For accuracy, as Visit 3 is to occur less than 10 days after Visit 2. | 
 • Table 5 |
| Allowed a window of ±10 days for Follow-up Visits | To allow sufficient flexibility | 
 • Table 5 |
| Deleted reporting of study-specific events | Not applicable as there are no criteria for study-specific events | 
 • Section 9.5.4.3 |
| Editorial corrections | For quality and consistency | 
 • Various locations |
| Changed visit window to ±6 instead of ±7 days in the Maintenance Period of the Extension Phase | Ensure that the shelf life of the investigational product is not exceeded. | 
 • Table 8 |

| Revisions to Version 3.0 New version/Date: v4.0, 22 Nov 2015 | | |
|--|---|---|
| Change | Rationale | Affected Protocol Sections |
| Revised testing for glucose and lipid panel to require fasting at baseline and end of treatment or early termination | In response to FDA request per persistent signal for weight gain and elevated triglycerides | 
• Table 2, Table 5, and Table 8 |

| Revisions to Version 2.0 New version/Date: v3.0, 27 Oct 2014 | | |
|---|---|---|
| Change | Rationale | Affected Protocol Sections |
| Revisions to grammar, spelling, etc. | Compliance with current company style guide and for general consistency | 
 • Throughout protocol |

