A laboratory abnormality may meet the criteria to qualify as an AE as described in this protocol (see [Section 9.5.1.5](#), Adverse Events and Events Associated with Special Situations) and the CRF Completion Guidelines. In these instances, the AE corresponding to the laboratory abnormality will be recorded on the Adverse Event CRF.

VITAL SIGNS AND WEIGHT MEASUREMENTS

Vital sign measurements (ie, systolic and diastolic blood pressure [BP] [mmHg], pulse [beats per minute], height, and weight (kg) will be obtained at the visits designated on the Schedule of Procedures/Assessments ([Table 5](#)) by a validated method. (revised per Amendment 01) Blood pressure and pulse will be measured after the subject has been sitting for 5 minutes. All BP measurements should be performed on the same arm, preferably by the same person.

OTHER SAFETY ASSESSMENTS

Pregnancy Test

A serum β -hCG test will be performed for postpuberty, premenopausal females and postmenopausal females who have been amenorrheic for less than 12 months. A 6-mL sample of

blood will be taken at designated timepoints as specified in the Schedule of Procedures/Assessments (Table 5).

Urine pregnancy testing will be conducted at timepoints specified in Table 5. (revised per Amendment 01)

CCI

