5.2.4 Demographic and Other Baseline Characteristics

Demographic and other baseline characteristics for the SAS will be summarized for each treatment group using descriptive statistics. Continuous demographic and baseline variables include age, weight, height and body mass index (BMI); categorical variables include sex, age group (2-<12, 12-<18, 18-<65, ≥65), race and ethnicity.

MEDICAL HISTORY

The number (percentage) of subjects reporting a history of any medical condition, as recorded on the case report form (CRF), will be summarized for the SAS for each treatment group and overall. A subject data listing of medical and surgical history will be provided.

Epilepsy-specific medical history for the SAS will be summarized for each treatment group and by age group using descriptive statistics, including time since diagnosis and seizure type.

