5.3.4 Examination of Subgroups

The following endpoints will be summarised by age (2-<12, 12-<18, 18-<65, ≥65):

Disposition; demography; epilepsy-specific medical history, number of baseline AEDs, baseline AEDs, compliance, percent change in drop, non-drop and total seizure frequency, 50%/75% response and seizure freedom rates in drop, non-drop and total seizures; clinical global impression exposure; treatment-emergent adverse events; change from baseline in laboratory values; treatment-emergent markedly abnormal laboratory values; change from baseline in vital signs; and Columbia Suicide Severity Rating Scale (C-SSRS), for subjects 8 years and over.

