5.6.4 Vital Signs

Descriptive statistics for vital signs parameters (diastolic and systolic blood pressure, pulse, respiration rate, temperature, weight, height) and changes from baseline to each post-baseline visit and to the last post-baseline visit will be presented by treatment group

In addition, the criteria described in [Table 1](#) will be used to determine clinically notable results for blood pressure and heart rate. The number (percentage) of subjects with clinically notable results over all scheduled and unscheduled visits will be summarized by treatment group.

Table 1: Criteria for Clinically Notable^a Vital Signs

Variable	Criterion Value	Change Relative to Baseline
Systolic BP	> 180 mmHg	Increase of ≥ 20 mmHg
	< 90 mmHg	Decrease of ≥ 20 mmHg

Diastolic BP	>105 mmHg	Increase of ≥ 15 mmHg
	< 50 mmHg	Decrease of ≥ 15 mmHg
Heart Rate	>120 bpm	Increase of ≥ 15 bpm
	< 50 bpm	Decrease of ≥ 15 bpm
Weight		Increase of $> 7\%$
		Decrease of $> 7\%$
a: Clinically notable means that a value must have met both the criterion value and satisfied the magnitude of change relative to baseline.		

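### SAP 5.6.4 lists a 7% weight-change criterion that its own lead-in sentence and footnote prevent from ever being counted

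*SAP*

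**What the plan says.** SAP 5.6.4 (Core Study) makes three statements that bear on notable weight.

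- **Lead-in sentence.** The Table 1 criteria "will be used to determine clinically notable results for blood pressure and heart rate". Weight is not named.
- **Table 1.** Weight has two rows, an increase and a decrease of more than 7% from baseline. The criterion-value cell is blank in both. Every blood pressure and heart rate row has one.
- **Footnote a.** "Clinically notable means that a value must have met both the criterion value and satisfied the magnitude of change relative to baseline".

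The same section also plans "Descriptive statistics for vital signs parameters (diastolic and systolic blood pressure, pulse, respiration rate, temperature, weight, height) and changes from baseline", by visit and arm. SAP 5.3.4 adds "change from baseline in vital signs" to the list of summaries by age band (2-<12, 12-<18, 18-<65, 65 and over). BMI appears in SAP 5.2.4 as a baseline variable only.

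In the protocol, the revision history for version 4.0 explains the move to fasting glucose and lipid samples as "In response to FDA request per persistent signal for weight gain and elevated triglycerides". Section 9.5.1.5 provides that "height, and weight (kg) will be obtained at the visits designated", and footnote h of Table 5 limits height to screening in adults only. Entry is from 2 years and 8 kg (Section 9.3.1).

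**The concern.** The weight rows have no purpose unless someone meant to count subjects who gain or lose more than 7%. Yet the lead-in leaves weight out, and the footnote sets a condition that weight cannot meet. A programmer must either produce an empty count or set the footnote aside on personal judgement. For a parameter with a recorded signal, that choice should be fixed in the SAP.

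A second, smaller issue remains once the wording is repaired. A single raw percentage applied from age 2 upward mixes ordinary growth with any drug effect, and so does raw change in kilograms. A child who merely stops gaining weight would not meet the decrease row.

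**Working it through.** **1. The rule itself.** The SAP attaches no figure to the weight analysis, so there is nothing to reproduce. The rule was applied under each reading to five test gains from baseline.

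| Reading | 3% | 6.9% | 7.1% | 10% | 25% | Flagged |
|---|---|---|---|---|---|---|
| Lead-in: blood pressure and heart rate only | no | no | no | no | no | 0 of 5 |
| Footnote a: both conditions, criterion blank | no | no | no | no | no | 0 of 5 |
| Blank cell means no criterion (overrides footnote a) | no | no | yes | yes | yes | 3 of 5 |

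The first two readings give zero whatever the data show. This result needs no assumption.

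**2. How much of the 7% growth could use.** The double-blind period is 6 + 12 = 18 weeks (Protocol 9.1). The documents give no growth rates, so these are assumptions: 2-2.5 kg a year at 12 kg and 2-3 kg a year at 20 kg.

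Percent growth = annual gain × (18 / 52.18) / baseline weight × 100.

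- 12 kg: 2 × 0.345 / 12 = 5.7%; 2.5 × 0.345 / 12 = 7.2%
- 20 kg: 2 × 0.345 / 20 = 3.4%; 3 × 0.345 / 20 = 5.2%

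On these rates growth uses about half to all of the limit, passing it only at the upper rate for the lighter child. Linear growth reaches 7% in 126 days at 7 × 365.25 / 126 = 20.3% a year.

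**3. Share of placebo subjects above 7%.** The assumptions are a normal distribution, an SD of 18-week change of 2-4 percentage points, and annual growth g (in %) as shown.

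Share = 1 − Φ[(7 − g × 126 / 365.25) / SD].

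| Annual growth | Share above 7% |
|---|---|
| 0% (adults) | 0-4% |
| 5% | 0.4-9% |
| 10% | 4-19% |
| 15% | 18-32% |
| 20% | 48-49% |

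**4. Effect on the arm comparison.** Assume an SD of 3 points and a drug effect of +1.5 points.

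| Mean growth over 18 weeks | Placebo above 7% | Drug above 7% | Difference | Ratio |
|---|---|---|---|---|
| 0 | 1.0% | 3.3% | 2.4 points | 3.4 |
| 5.2% | 27% | 46% | about 19 points | 1.7 |

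With growth the risk difference rises and the ratio falls.

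**5. Whether another visible analysis fills the gap.** Protocol 9.7.1.8 names only blood pressure and pulse for the Core vital-sign summary. Weight is not among the special-interest events in SAP 5.6.2.2. No post-baseline BMI, z-score or percentile appears in the readable text.

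**The case against.** The most natural reading of a blank criterion cell is that no criterion applies; otherwise the rows are pointless. Table shells and derivation rules are held in separate documents (SAP Sections 9 and 11) and may already settle the matter. This is fair as to intent, but the SAP states the opposite in the footnote and omits weight from the lead-in. The contradiction therefore stands, and correcting it is trivial.

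Other analyses give partial cover. Change in weight and height is summarised by visit and arm, change in vital signs is also split by age, and a weight event reported as an adverse event enters the tables by arm and age group (SAP 5.6.2). These points stand. However, the 2-<12 band is too wide to remove growth, and adverse-event tables capture only what an investigator reports. SAP 5.7.1-5.7.4 and Protocol 9.5.1.6 are redacted, so the absence of any growth analysis cannot be confirmed.

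The recorded request led to fasting glucose and lipid sampling. A reader might infer that the regulator asked for a weight-outlier or growth-standardised analysis; the protocol does not say so. It shows only that a weight-gain signal was known.

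A reader might also infer that growth pulls the arm comparison toward no difference. The design does not support that. Allocation is 1:1 against concurrent placebo and stratified by age group (Protocol 9.4.3), so growth is expected equally in both arms and the difference in mean change is not biased. For threshold counts, the illustration shows the risk difference widening.

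**Conclusion.** As written, the notable-weight count in SAP 5.6.4 is empty by construction under either the lead-in or the footnote. That is a wording contradiction in a safety rule, on a parameter with a recorded signal, and it should be corrected. It rests on the text alone.

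The growth point is secondary and depends on assumed rates: about 3.4-7.2% over 18 weeks at 12-20 kg. Its consequences are added variability, a diluted ratio of notable counts, and within-arm rates in young children that are hard to interpret without the placebo column. The calculation covers only two body weights. The documents give no age distribution, so it does not show that most flagged subjects would be children growing normally.

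It is tempting to carry the growth arithmetic into Extension A and conclude that nearly every young child would be flagged. No such count is planned: the 7% rule sits in the Core SAP, and the Extension SAP (5.5.4) only lists vital signs.

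**What to change.** **Correction.** In SAP 5.6.4, make the lead-in read *blood pressure, heart rate and weight*, and add to footnote a that for weight the change criterion alone applies. The cost is two short edits; SAP Section 7 already provides for later changes to be documented separately and addressed in the study report.

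**Cheap addition.** For subjects under 18, add a descriptive summary by arm and age group of change from baseline in age- and sex-standardised weight, height and BMI z-scores. Height and weight are already measured at scheduled visits, and age and sex are collected (Protocol 9.5.1.1), so no new data are needed. The cost is naming a growth reference and some extra programming. Protocol 9.5.1.1 accepts date of birth or age; if only whole years are held, scores in the youngest will be less precise. The documents support no particular z-score cut-off, so whether to use one, and which, is for the sponsor to decide.

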5.6.5 Electrocardiograms

12-lead ECG will be obtained at the Screening Visit only. Since the data are not planned to be included in the database, no ECG summaries will be produced.

5.6.6 Other Safety Analyses

5.6.6.1 C-SSRS

Scoring of the C-SSRS will be performed as suggested by the C-SSRS Columbia website http://www.cssrs.columbia.edu/clinical_trials.html.

The following summaries will be presented for the treatment duration (defined as the period from the date of first dose up to 28 days after the date of last dose, inclusive).

- Number (percentage) of subjects with any treatment-emergent report of suicidal behavior, suicidal ideation, and suicidality (suicidal behavior and/or ideation) will be displayed. A treatment-emergent report of suicidal behavior, suicidal ideation, or suicidality is an answer of 'Yes' to any question in the respective category during the treatment duration.
- Shift from baseline to the maximum suicidal ideation severity rating (0=no ideation present to 5=active ideation with plan and intent) in the treatment duration will assess worsening of suicidal ideation. Any score greater than 0 indicates the presence of suicidal ideation while a score of 4 (active suicidal ideation with some intent to act) or 5 (active suicidal ideation with specific plan and intent) can be used to indicate serious suicidal ideation.

Descriptive statistics and changes from baseline will be presented by visit for the suicidal ideation severity rating (treated as a continuous variable) to assess change in suicidal ideation over time.
Other Analyses

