9 INVESTIGATIONAL PLAN

9.1 OVERALL STUDY DESIGN AND PLAN

This will be a multicenter, double-blind, randomized, placebo-controlled, parallel-group study of perampanel as adjunctive therapy in subjects with inadequately controlled seizures associated with LGS. The study will consist of 3 phases: Prerandomization, Randomization, and Extension. The Core Study will consist of the Prerandomization and Randomization Phases.

The Prerandomization Phase will consist of a 4- to 8-week Screening/Baseline Period during which subjects will be assessed for overall eligibility to participate in the study, including seizure activity. Baseline seizure count will be assessed using all diary data before randomization (at least 4 weeks prospectively). Following successful completion of this period, subjects will be randomized to receive perampanel or placebo in a 1:1 ratio.

The Randomization Phase will consist of 3 periods: Titration (6 weeks), Maintenance (12 weeks), and Follow-up (4 weeks, only for subjects not entering into Extension A). As required by some regulatory agencies, the following estimates are provided:

- The study will begin approximately Jan 2017 and will end approximately Jan 2020. (revised per Amendment 01)
- The maximum estimated period for each subject (except subjects continuing in Extension B) on the study is anticipated to be approximately 82 weeks. (revised per Amendment 04)

An overview of the study design is presented in [Figure 1](#).

[figure not shown]

Figure 1 Study Diagram for Study E2007-G000-338 (revised per Amendment 04)

R = randomization.

a: Subjects who do not continue in Extension A or those who prematurely discontinue from the study will return to the study site for Follow-up visits 1 week and 4 weeks after the last study drug administration.

b: Subjects will be up-titrated to optimize efficacy while maintaining good tolerability, up to a maximum dose of 8 mg/day. Once titrated, all subjects will be kept at a stable dose for at least 2 weeks (to reach steady-state) before the start of the Maintenance Period. The dose of study drug during the Maintenance Period will be the last dose achieved at the end of the Titration Period.

c: After the double-blind Conversion Period of Extension A, subjects can be titrated (except in Japan, where the maximum allowed dose remains at 8 mg/day) up to 12 mg/day in 2-week intervals, as per the investigator's discretion.

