9.5.2 Schedule of Procedures/Assessments Core Study

Table 5 presents the Schedule of Procedures/Assessments for the Core Study.

Table 5 Schedule of Procedures/Assessments in Study E2007-G000-338 (Core Study)

(revised per Amendments 01, 04, and 05)

| Phase | Prerandomization | Randomization | | | | | | | | | |
|---|------------------|---------------------|------------------------|----|----|--------------------------|-----|----------------|----------|--------------------------------|---------------------------------|
| | | Screening/Base line | Titration ^a | | | Maintenance ^b | | | Early DC | Follow-up | |
| Visit | 1 ^a | | 2 ^c | 3 | 4 | 5 | 6 | 7 ^d | | Follow-up, 1 week ^e | Follow-up, 4 weeks ^e |
| Week | (up to -8) | 1 | 2 | 4 | 7 | 13 | 19 | | 20 | 23 | |
| Day | (up to -56) | 1 | 8 | 22 | 43 | 85 | 127 | | 134 | 155 | |
| Procedures/ Assessments | | | | | | | | | | | |
| Informed consent/assent | X | | | | | | | | | | |
| Inclusion/exclusion | X | X ^f | | | | | | | | | |
| Randomization | | X ^f | | | | | | | | | |
| Physical and neurological examination | X | | | | | | | | | | |
| Medical history ^g | X | | | | | | | | | | |
| Prior/concomitant medications | X | X | X | X | X | X | X | X | X | X | X |
| Vital signs, height and weight ^h | X | X | X | X | X | X | X | X | | X | (X) ⁱ |
| ECG | X | | | | | | | | | | (X) ⁱ |
| CCI | | | | | | | | | | | |
| C-SSRS ^k | X | | | | | X | | X | | X | (X) ⁱ |

Table 5 Schedule of Procedures/Assessments in Study E2007-G000-338 (Core Study)

(revised per Amendments 01, 04, and 05)

| Phase | Prerandomization | Randomization | | | | | | | | | |
|--|---------------------|------------------------|---|----|--------------------------|----------------|----------------|----------------|--------------------------------|---------------------------------|------------------|
| Period | Screening/Base line | Titration ^a | | | Maintenance ^b | | | Early DC | Follow-up | | Unscheduled |
| Visit | 1 ^a | 2 ^c | 3 | 4 | 5 | 6 | 7 ^d | | Follow-up, 1 week ^e | Follow-up, 4 weeks ^e | |
| Week | (up to -8) | 1 | 2 | 4 | 7 | 13 | 19 | | 20 | 23 | |
| Day | (up to -56) | 1 | 8 | 22 | 43 | 85 | 127 | | 134 | 155 | |
| Procedures/ Assessments | | | | | | | | | | | |
| Urine pregnancy test ^l | | X | X | X | X | X | X | X | | X | (X) ⁱ |
| Serum pregnancy test ^l | X | | | | | | | | | | |
| Clinical laboratory tests ^m | X | X ⁿ | | X | | | X ⁿ | X ⁿ | | X | (X) ⁱ |
| Viral tests (HBsAg, HepC) | X | | | | | | | | | | |

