- e: Only for those subjects not rolling over into Extension A, and for those subjects who prematurely discontinued from the study, the Follow-up visits will take place at 1 week and 4 weeks after the last study drug administration (ie, Visit 7 or Early Discontinuation Visit, respectively). These visits will not be conducted if the subject continues into Extension A, in which case, a Follow-up visit will be performed 4 weeks after the last Extension visit. Visits will have a window of ± 6 days. (revised per Amendments 01 and 04)
- f: Final determination of eligibility and, if eligible, randomization to occur before any study drug administration. (revised per Amendment 04)
- g: Lifetime AED history will be collected as part of medical history.
- h: Height of adult subjects is to be recorded only at the Screening Visit (Visit 1). (revised per Amendment 01)
- i: CCI [REDACTED]
- j: [REDACTED]
- k: Subjects ≥ 8 years of age at time of informed consent/assent and subjects who will reach the age of 8 years during the double-blind phase of the study will also be assessed using the C-SSRS starting at Baseline. (revised per Amendment 03)
- l: Urine and serum pregnancy testing is for postpuberty, premenopausal females and postmenopausal females who have been amenorrheic for less than 12 months.
- m: Clinical laboratory tests include chemistry, hematology, and urinalysis. If a urine sample cannot be obtained; the subject will still be eligible for enrollment. However, every effort should be made to collect a sample.
- n: Fasting samples to be taken at indicated time points for glucose and lipid panel.
- o: Drug screen includes cocaine, phencyclidine [(PCP)], opioids ([as a group]), benzodiazepines, barbiturates, and amphetamines. Positive CBD results in subjects taking CBD products will not be exclusionary. (revised per Amendment 04)
- p: Collect diaries at Visit 7 from subjects not rolling over into Extension A. Dispense diaries at Visit 7 to subjects rolling over into Extension A.
- q: CCI [REDACTED]

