If the window is not the baseline or the follow-up assessment, then the assessment closest to the scheduled assessment will be used in the summary tables. Note that if two assessments are equidistant from the scheduled assessment then the earliest assessment of the two (within the allowable window) will be used. .

Table 1: Mapping of Study Day Ranges to Week for Vital Signs and Weight

Windowing Period	Study Day Range (Relative to First Dose)	Week
Pretreatment	Day $\leq 1^a$	0
Treatment	$2 \leq \text{Day} \leq 20$	2
Treatment	$21 \leq \text{Day} \leq 31$	4
Treatment	$32 \leq \text{Day} \leq 66$	7
Treatment	$67 \leq \text{Day} \leq 104$	12
Treatment	$105 \leq \text{Day} \leq 140$	18
	Day Relative to 14 Days After Last Dose	
Post-Treatment	Day $\leq 999^c$	4

- a: All assessments performed on the same date as the date of first dose were to be performed prior to dosing; results from these assessments will be regarded as Pretreatment values in the analyses.
- b: Measurements must have been taken during the treatment duration, ie, within 14 days of the day of last dose, to be included in analyses as on-treatment assessments.
- c: Measurements must have been taken more than 14 days after the day of last dose to be included in analyses as Post-treatment assessments. Target day is 28 days after last dose or Post-treatment Week 4.

It should be noted that for the post-treatment duration, the study week window is defined relative to the last dose, rather than to the first dose.

Table 3: Mapping of Study Day Ranges to Week for Laboratory Assessments

Windowing Period	Study Day Range (Relative to First Dose)	Week
Pretreatment	Day $\leq 1^a$	0
Treatment	$2 \leq \text{Day} \leq 76$	4
Treatment	$77 \leq \text{Day} \leq 140$	18
	Day Relative to 14 Days After Last Dose	
Post-Treatment	Day $\leq 999^c$	4

- a: All assessments performed on the same date as the date of first dose were to be performed prior to dosing; results from these assessments will be regarded as Pretreatment values in the analyses.
- b: Measurements must have been taken during the treatment duration, ie, within 14 days of the day of last dose, to be included in analyses as on-treatment assessments.
- c: Measurements must have been taken more than 14 days after the day of last dose to be included in analyses as Post-treatment assessments. Target day is 28 days after last dose or Post-treatment Week 4.

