5.5.6 Other Safety Analyses

5.5.6.1 C-SSRS

The following summary will be presented for the treatment duration (defined as the period from the date of first dose up to 28 days after the date of last dose, inclusive) .

Number (percentage) of subjects with any treatment-emergent report of suicidal behavior, suicidal ideation, and suicidality (suicidal behavior and/or ideation) will be displayed. A treatment-emergent report of suicidal behavior, suicidal ideation, or suicidality is an answer of 'Yes' to any question in the respective category during the treatment duration.

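### The C-SSRS window closes on the target day of the 4-week follow-up, so compliant visits 1 to 6 days late drop out of the suicidality count and the ideation shift

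*SAP*

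**What the plan says.** Core SAP section 5.6.6.1 ties two C-SSRS summaries to a "treatment duration (defined as the period from the date of first dose up to 28 days after the date of last dose, inclusive". They are the number of subjects with treatment-emergent suicidal ideation or behavior, and the shift from baseline to the highest ideation rating. By-visit statistics for the ideation rating follow, and the limit is not restated for them. Extension SAP section 5.5.6.1 presents only the count, over the same "period from the date of first dose up to 28 days after the date of last dose".

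In Protocol section 9.5.2, Table 5 as extracted places a C-SSRS at the 4-week follow-up and none at the 1-week follow-up. Footnote e says "Follow-up visits will take place at 1 week and 4 weeks after the last study drug administration (ie, Visit 7 or Early Discontinuation Visit" and adds "Visits will have a window of ± 6 days". The study-day row reads "1 | 8 | 22 | 43 | 85 | 127 | | 134 | 155", so Visit 7 is Day 127 and the 4-week follow-up is Day 155. Protocol section 9.1 lists the periods as "Titration (6 weeks), Maintenance (12 weeks), and Follow-up (4 weeks, only for subjects not entering into Extension A"; early discontinuers also have the follow-up visits.

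For vital signs and laboratory data, the notes to the window tables in Core SAP section 8.2.2 say "Target day is 28 days after last dose or Post-treatment Week 4".

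For Extension A, Protocol Appendix 2 (Table 8) puts Visit 14 on Day 491 and the follow-up on Day 519. It marks a C-SSRS at both and allows 6 days either way.

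**The concern.** The analysis window and the visit schedule use the same 28 days, but only the schedule has a tolerance. Two subjects can both attend within the protocol's window and give the same answer, yet one is counted and the other is not.

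The form of the data makes this worse than it would be for adverse events. An adverse event is placed by its onset. A C-SSRS report counts only if the answer is given inside the window. Ideation that began 10 days after stopping, but was first reported at a compliant visit on day 30, is outside both summaries.

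The people affected are those who stop treatment. Protocol section 9.3.3 withdraws subjects judged at high risk of suicidal behavior, so leavers are a relevant group. As extracted, Table 5 also shows no C-SSRS at Visit 7 (columns may have shifted in extraction). If that reading is right, a completer who does not enter Extension A has no scheduled C-SSRS between Visit 6 (Day 85) and the follow-up (Day 155), a gap of 155 − 85 = 70 days. A late follow-up would then be that subject's only assessment after Day 85.

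**Working it through.** **Inputs**
- Cutoff: last dose + 28 days, inclusive (Core SAP 5.6.6.1; Extension SAP 5.5.6.1).
- Visit 7: Day 127. 4-week follow-up: Day 155 (Protocol Table 5).
- Visit tolerance: 6 days either way (Table 5, footnote e), giving 2 × 6 + 1 = 13 allowed days.
- Extension A: Visit 14 on Day 491, follow-up on Day 519 (Table 8).

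**The plan's own figure.** 155 − 127 = 28 days. This reproduces the SAP's 28-day post-treatment target and the protocol's 4 weeks. Because the cutoff is inclusive, a visit exactly on target is counted.

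**Allowed days past the cutoff.** With L the day of last dose, the on-time visit is t = 155 − L, the allowed range is t − 6 to t + 6, and a day is excluded if it exceeds 28.

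| Day of last dose | On time | Allowed range | Excluded days | Share |
|---|---|---|---|---|
| 127 (Visit 7, per footnote e) | 28 | 22 to 34 | 29 to 34 | 6/13 = 46.2% |
| 126 (evening before Visit 7) | 29 | 23 to 35 | 29 to 35 | 7/13 = 53.8% |

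The second row is an assumption. It rests on bedtime dosing, on 18 weeks being 126 days, and on unused drug being collected at Visit 7 with on-site dosing marked only at Visits 5 and 6. No section gives the calendar day of the last dose, and footnote e equates last administration with Visit 7.

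**Extension A.** 519 − 491 = 28, and 519 − 490 = 29 if the last dose is the evening before Visit 14. With the same tolerance the counts are again 6 or 7 of 13.

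**From days to visits.** The shares above are of calendar days. They equal shares of visits only if attendance is uniform over the 13 days. The documents give no attendance pattern. As a range, assume instead that attendance is symmetric about the target, with weight exp(−(x − t)²/(2·SD²)) on each allowed day x:

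| SD (days) | Last dose Day 127 | Last dose Day 126 |
|---|---|---|
| 1 | 30.1% | 69.9% |
| 2 | 40.0% | 60.0% |
| 3 | 43.1% | 56.9% |

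On the protocol's own anchor, fewer than half of compliant visits fall outside under any of these patterns.

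**The case against.** The strongest defence is that 28 days is deliberate. Core SAP section 8.2.2 ends the adverse-event treatment duration at 28 days after the last dose, and the protocol defines treatment-emergent events the same way. One limit for everything called treatment-emergent is coherent, and a longer one for the C-SSRS would break that symmetry. This stands as a reason for choosing 28 days. It does not answer the mismatch, because an adverse event enters by onset and a C-SSRS answer by the date it was given.

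There are other safeguards. Table 5 has a C-SSRS at the Early Discontinuation visit. Table 8 has one there and at Visit 14. Core SAP section 5.6.2.2 lists and summarizes suicidality-related adverse events, and serious events are collected for 28 days after the last dose. These reduce what can be missed, but an answer recorded only on the follow-up C-SSRS still does not reach the count. The Core by-visit statistics state no 28-day limit, so a late rating may appear there. It would be part of a mean, which does not replace a count of subjects. The Extension SAP has no such second summary; its section 7 explains that output is limited because the study ended early.

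A reader might go further and infer that even an on-time follow-up falls on day 29, that compliant visits run to day 35, and that most of these assessments are discarded. The documents do not support this. The first two need a last dose on Day 126, which is plausible but unstated and conflicts with footnote e. Where the visit is timed from the actual last dose, on time is day 28 and the latest compliant day is 34. On the protocol's anchor, 6 of 13 days is a minority. Nor are the data discarded: they are left out of specific summaries.

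**Conclusion.** The point holds as a mismatch between an analysis window and a visit window. Compliant follow-up C-SSRS assessments on days 29 to 34 are left out of the treatment-emergent count and the maximum-ideation shift in the Core SAP, and out of the only C-SSRS summary in the Extension SAP. The exclusion covers 6 of 13 allowed days. It covers 7 of 13, including the nominal day, if the last dose is taken the evening before the final treatment visit.

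The reach is limited. It concerns C-SSRS-assessed subjects who do not continue to the next phase and who attend after day 28. Their number cannot be derived from the documents. A count changes only if the late visit gives a positive answer, or a higher rating, not already seen in the window. The rule is the same in both arms, and any resulting error is an undercount. The reading that this is the only scheduled post-treatment Core C-SSRS depends on the extracted layout of Table 5.

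**What to change.** In Core SAP section 5.6.6.1 and Extension SAP section 5.5.6.1:

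1. Assign the scheduled 4-week follow-up C-SSRS by visit. Include it in the windowed summaries whenever it was done within its protocol visit window, for subjects who did not continue to the next phase.
2. State which date counts as last dose for this purpose: the recorded study-drug end date or the date of the final treatment visit. Core SAP section 8.1.2 takes it from the study medication CRF page, but that text sits in the efficacy rules.

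The cost is one date rule and a sentence of definition in each plan, using data already collected. The one downside is small: the C-SSRS window becomes a few days longer than the 28-day adverse-event window, which a table footnote can state.
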